7.1.4.4.2 Time to improvement of 80 mL in FEV1

This is defined as the time (in days) from initiation of study treatment until the change in FEV1 is $\geq +80$ mL (improvement).

Change in FEV1 = FEV1 value (time T) – FEV1 value (baseline).

Table 2-2: Criteria for event/censored for assessment of Time to improvement of 80 mL (FEV1)

Situation	Date of event or Censoring	Time to improvement of 80 mL	Outcome
Subjects who meet criteria of change in FEV1 $\geq + 80$ mL	Date when the criteria is met	Time from initiation of study treatment until Date when the aforesaid criteria is met	Event
Subjects who never meet change in FEV1 $\geq + 80$ mL	Date of the last evaluable spirometry	Time from initiation of study treatment until Date of the last evaluable spirometry	Censored
Subjects who died	Death date	Time from initiation of study treatment until Date of death	Censored
Subjects who withdrew or were lost to follow-up during the study	Withdrawal or last contact date	Time from initiation of study treatment until Date of withdrawal or last contact date	Censored

7.1.4.5 Standardised Area Under Curve (AUC) of FEV1

AUC will be calculated according to the trapezoidal rule. The trapezoidal rule is a numerical method to be used to approximate the integral or the area under a curve. Using trapezoidal rule to approximate the area under a curve first involves dividing the area into a number of strips of equal width. Then, approximating the area of each strip by the area of the trapezium formed when the upper end is replaced by a chord. The sum of these approximations gives the final numerical result of the area under the curve.

The (standardised) AUC of the FEV1 will be calculated from Day (a) to Day (b) using the trapezoidal rule as follows:

$$AUC(a,b) = \left(\sum_{x=a+1}^b \frac{(Y_{x-1} + Y_x)(x - (x-1))}{2} \right) \left(\frac{1}{b-a} \right)$$

where x = Actual day of measurement and Y_x = FEV1 value at Day x

Missing values for the calculation of FEV1 AUC will be handled as follows:

- If single or more intermediate values are missing between two non-missing values, they will be ignored and the component of the AUC will be calculated between 2 days for this part of the curve.
- If FEV1 value at Day 1 pre-dose (baseline) is missing then the AUC will be missing.

- For the Day 1 – 3 AUC, Day 1 – 7 AUC, Day 1 – 10 AUC and Day 1 – 14 AUC: if < 50% of values are available from Day 1 pre-dose (baseline), then the AUC will be set as missing.

7.1.4.6 Respiratory Rate (RR) normalisation

RR is normalised if RR returns to a baseline plateau level achieved after the acute COPD exacerbation during the Stabilisation Phase. This baseline plateau value is defined on a patient basis, and corresponds to the mean of the 3 RR values recorded during the Stabilisation Phase for each patient (mean of RR at Weeks 8, 12 and 26). Only 1 of the 3 data points needs to be present for this computation. In the case that all three RR values are missing during the Stabilisation Phase for a patient, the baseline plateau value will be set to 20 breaths/min².

To summarise, RR is normalised if RR returns to a value $\leq P$ breaths/min; where P (“Plateau”) equals to:

- mean of RR at Weeks 8, 12 and 26 (on a patient basis)
- 20 breaths/min, if all three RR values at Weeks 8, 12 and 26 are missing.

7.1.4.7 Questionnaire EXACT-PRO

The EXACT is a 14-item patient reported outcome (PRO) daily diary used to quantify and measure exacerbations of COPD (Mackay 2014⁴). This instrument provides a single, standardised approach for assessing the symptomatic manifestations of COPD exacerbations, with a development and validation history consistent with guidelines proposed by the FDA, EMA and well-known measurement principles.

The questionnaire is composed of 14 items covering various domains such as breathlessness, cough and sputum, chest symptoms, and overall status (tiredness, weakness, sleep disturbances). Each question is individually weighted to provide a total score varying from 0 to 100. The health status of the subject is correlated to the global score, meaning a higher score corresponds to a more severe health status of the subject.

The EXACT-PRO will be completed once a day in the evening by the subject. The EXACT score will be monitored and will raise an alert to the investigator in case of relevant increases.

EXACT Total Score

An EXACT Total score is computed for each day of diary collection. The EXACT Total score is based on a logit scoring system with conversion to a 0 to 100 scale for ease of interpretation and use. The total score is used in the determination of exacerbation frequency, severity and duration of exacerbation. Specifically, changes in the total score are used to define onset and recovery from an exacerbation event and the magnitude of that event.

EXACT Domain Scores

Additional information regarding the patient's condition can be obtained through 3 domain scores embedded within the EXACT measure: Breathlessness, Cough & Sputum, and Chest Symptoms. These scores also range from 0 to 100 with higher scores indicating more severe symptoms.

Appendix C describes the EXACT raw scores and EXACT scoring instructions to compute the EXACT daily scores and event frequency, duration and severity.

7.1.4.8 Time to improvement/recovery based on EXACT-PRO total score

Table 3: Criteria for event/censored for assessment of Time to improvement/recovery (EXACT-PRO)

Situation	Date of event or Censoring	Time to improvement/recovery (EXACT-PRO)	Outcome
Subjects who had current COPD exacerbation improved/recovered over the observed period	Date of improvement/recovery of current COPD exacerbation	Time from initiation of study treatment until Date of improvement/recovery of current COPD exacerbation	Event
Subjects who never had current COPD exacerbation improved/recovered over the observed period	Date of the last evaluable EXACT-PRO assessment	Time from initiation of study treatment until Date of the last evaluable EXACT-PRO assessment	Censored
Subjects who died over the observed period	Death date	Time from initiation of study treatment until Date of death	Censored
Subjects who withdrew or were lost to follow-up over the observed period	Withdrawal or last contact date	Time from initiation of study treatment until Date of withdrawal or last contact date	Censored

7.1.4.9 Standardised AUC of EXACT-PRO Total Score

The (standardized) AUC of the EXACT-PRO will be calculated from Day (a) to Day (b) using the trapezoidal rule as follows:

$$AUC(a,b) = \left(\sum_{x=a+1}^b \frac{(Y_{x-1} + Y_x)(x - (x-1))}{2} \right) \left(\frac{1}{b-a} \right)$$

where x = Actual day of measurement and Y_x = Rolling average at Day x .

AUCs for EXACT-PRO subscores will also be calculated.

Missing values for the calculation of EXACT-PRO score and subscores AUCs will be handled as follows:

- If single or more intermediate value is missing between two non-missing values, they will be ignored and the component of the AUC will be calculated between 2 days for this part of the curve.
- If baseline EXACT-PRO rolling average (i.e. EXACT-PRO score at Day 1) is missing then the AUC will be missing.
- For the Day 1 – 3 AUC:
 - o if < 50% of rolling average values are available from Day 1, then the AUC will be set as missing.
 - o if the rolling average is missing at Day 3 then the average between the Rolling Average at Day 2 and the Rolling Average at Day 4 will be used in the AUC calculation in place of the Rolling Average at Day 3.
- For the Day 1 – 5 AUC:
 - o if < 50% of rolling average values are available from Day 1, then the AUC will be set as missing.
 - o if the rolling average is missing at Day 5 then the average between the Rolling Average at Day 4 and the Rolling Average at Day 6 will be used in the AUC calculation in place of the Rolling Average at Day 5.
- For the Day 1 – 7 AUC:
 - o if < 50% of rolling average values are available from Day 1, then the AUC will be set as missing.
 - o if the rolling average is missing at Day 7 then the average between the Rolling Average at Day 6 and the Rolling Average at Day 8 will be used in the AUC calculation in place of the Rolling Average at Day 7.
- For the Day 1 – 10 AUC:
 - o if < 50% of rolling average values are available from Day 1, then the AUC will be set as missing.
 - o if the rolling average is missing at Day 10 then the average between the Rolling Average at Day 9 and the Rolling Average at Day 11 will be used in the AUC calculation in place of the Rolling Average at Day 10.
- For the Day 1 – 14 AUC:
 - o if < 50% of rolling average values are available from Day 1, then the AUC will be set as missing.
 - o if the rolling average is missing at Day 14 then the average between the Rolling Average at Day 13 and the Rolling Average at Day 15 will be used in the AUC calculation in place of the Rolling Average at Day 14.

- For the Day 1 – 29 AUC:
 - o if the rolling average is missing at Day 29 no further imputation will be performed and the Day 29 will be considered missing in the calculation of the AUC.

7.1.4.10 Time to next COPD exacerbation

The time to next COPD exacerbation (in days) is defined as:

(Date when first COPD exacerbation symptoms started – Date when current COPD exacerbation symptoms stopped),

where COPD exacerbations experienced during the study are recorded on the ‘Acute Exacerbation COPD’ form of the eCRF, i.e.:

- Start date of COPD exacerbation is the ‘date when symptoms started’ recorded on the form
- COPD exacerbation has an intensity recorded as ‘Mild’, ‘Moderate’ or ‘Severe’ on the form.

Table 4: Criteria for event/censored for assessment of Time to next COPD exacerbation

Situation	Date of event or Censoring	Time to next COPD exacerbation	Outcome
Subjects who had next COPD exacerbation	Date of next COPD exacerbation after entering in study	Time from when current COPD exacerbation symptoms stopped until Date of next COPD exacerbation after entering in study	Event
Subjects who never had COPD exacerbation in study period	Withdrawal or last contact date	Time from when current COPD exacerbation symptoms stopped until Date of withdrawal or last contact date	Censored
Subjects who died	Death date	Time from when current COPD exacerbation symptoms stopped until Date of death	Censored
Subjects who withdrew or were lost to follow-up during the study	Withdrawal or last contact date	Time from when current COPD exacerbation symptoms stopped until Date of withdrawal or last contact date	Censored

7.1.4.11 Time from hospitalisation admission until subject is medically ready for discharge (current COPD)

This time (in days) will be calculated as:

(Date subject is medically ready for discharge from hospital – Date of hospitalisation admission),

where ‘Date of hospitalisation admission’ and ‘Date subject is medically ready for discharge from hospital’ are recorded on the ‘Current COPD Exacerbation’ form of the eCRF.

Table 5: Criteria for event/censored for assessment of Time from hospitalisation admission until subject is medically ready for discharge (current COPD)

Situation	Date of event or Censoring	Time from hospitalisation admission until subject is medically ready for discharge	Outcome
Subjects who were medically ready for discharge from hospital	Date subject is medically ready for discharge	Time from hospitalisation admission until Time subject is medically ready for discharge	Event
Subjects who were not medically ready for discharge from hospital	Withdrawal or last contact date	Time from hospitalisation admission until Date of withdrawal or last contact date	Censored
Subjects who died	Death date	Time from hospitalisation admission until Date of death	Censored
Subjects who withdrew or were lost to follow-up during the study	Withdrawal or last contact date	Time from hospitalisation admission until Date of withdrawal or last contact date	Censored

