7 INTRODUCTION

7.1 Background

Chronic obstructive pulmonary disease (COPD) is a progressive condition that is a major cause of poor health and death worldwide ([GOLD Guidelines 2015](#)) and contributes significantly to health care costs and comorbidity ([Lopez et al 2006](#)), ([Chapman et al 2006](#)). COPD is a chronic disease for which worldwide prevalence (currently estimated at 210 million) and mortality rate (2.74 million died in 2000) are still increasing. COPD is currently ranked as the fourth cause of death ([GOLD Guidelines 2015](#)) and is anticipated to become the third by 2020.

COPD exacerbations account for 50-75% of the cost of healthcare services in COPD ([Mittmann et al 2008](#), [Toy et al 2010](#)). The impact of the exacerbations on patient's overall well-being is significant, and the symptoms and deterioration in lung function may persist for several weeks before recovering to Baseline values ([Seemungal et al 2000](#)). On average, COPD patients experience approximately 1-3 exacerbations per year, although this varies with the severity of underlying COPD ([Seemungal et al 2009](#); [Langsetmo et al 2008](#)). A median duration of exacerbation of 13 (6 to 24) days has been reported in patients receiving SoC, and 9 (6 to 14) days in patients receiving long-term therapy with macrolide antibiotics in addition to SoC. Of these exacerbations, 37% (patients treated with long-term macrolides in addition to SoC) and 60% (patients treated with SoC) had not resolved within 10 days ([Seemungal et al 2008](#)). A recent retrospective observational database study showed a median duration of hospital stay due to moderate to severe COPD exacerbation of 9 to 10 days ([Molinari et al 2015](#)). Based on published literature, approximately 32% of exacerbations occur within 8 weeks of a preceding exacerbation event ([Hurst 2009](#)), and approximately 60% of patients are readmitted to the hospital within 12 months because of an exacerbation ([Almagro et al 2006](#); [Garcia-Aymerich et al 2003](#); [Lau 2001](#)), highlighting the need for more effective treatments.

Since frequent COPD exacerbations are known to promote disease progression ([Donaldson 2002 et al](#); [Rennard and Farmer 2004](#)), there is a high unmet need for more effective treatment to reduce the number and severity of exacerbations as well as the length and number of hospitalisations.

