7.1.4.14 Time to clinical treatment failure

The time to clinical treatment failure (in days) is defined as:

(Date when any one of the criteria defining the composite endpoint occurred for the first time – Date of initiation of study treatment),

where acute COPD exacerbations experienced during the study and their characteristics are recorded on the 'Acute Exacerbation COPD' form of the eCRF, i.e. in particular:

- Date of first antibiotic intake and/or first systemic corticosteroid intake for treating the COPD exacerbation
- Date of hospitalisation admission for the COPD exacerbation
- Date of emergency room admission (emergency room admission for longer than 24 hours will qualify as a hospitalisation) for the COPD exacerbation
- Date the COPD exacerbation (assessed as an AE) results in death.

Table 6: Criteria for event/censored for assessment of Time to clinical treatment failure

Situation	Date of event or Censoring	Time to clinical treatment failure	Outcome
Subjects who had any one of the criteria defining the composite endpoint	Date of clinical treatment failure after entering in study	(Time from initiation of study treatment until Date of clinical treatment failure after entering in study)	Event
Subjects who never had any one of the criteria defining the composite endpoint in study period	Withdrawal or last contact date	(Time from initiation of study treatment until Date of withdrawal or last contact date)	Censored
Subjects who died (not COPD-related)	Death date	(Time from initiation of study treatment until Date of death)	Censored
Subjects who withdrew or were lost to follow-up during the study	Withdrawal or last contact date	(Time from initiation of study treatment until Date of withdrawal or last contact date)	Censored

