7.2.2.2 Partial dates of current COPD exacerbation symptoms start/stop

In order to calculate the current COPD exacerbation duration (i.e. from the date when symptoms started until the date when symptoms stopped) and the times from start/stop of current COPD exacerbation to first dosing, the following rules will be applied for partial dates for current COPD exacerbation symptoms start and stop:

- if the day of the month is missing it is imputed to be the 15th
- missing months will be left as missing
- missing years will be left as missing.

The above will be flagged and described as a footnote in the appropriate listings.

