The following figures will be produced for the EXACT-PRO rolling average score:

- Mean EXACT-PRO rolling average score over time by treatment regimen (Acute Exacerbation Phase and Stabilisation Phase separately).
- Mean EXACT-PRO rolling average score change from baseline over time by treatment regimen (Acute Exacerbation Phase and Stabilisation Phase separately).

The same analysis as above will be performed for each of the 3 EXACT-PRO subscores.

8.6.3.11 Number of COPD-related exacerbations during the study derived from 'Acute Exacerbation COPD' form of the eCRF

COPD-related exacerbations during the study derived from the 'Acute Exacerbation COPD' form of the eCRF will be considered for this analysis.

Only COPD exacerbations with symptoms start date \geq first study treatment intake on the form will be included in the analysis. The ‘date when symptoms started’ recorded on the form will be defined as the start date of the COPD exacerbation.

The number and the percentage of patients with COPD exacerbations, the number of COPD exacerbations and the total follow-up time in years will be summarised by treatment regimen.

The rate of COPD exacerbations per patient per year will be calculated for each treatment regimen using a weighted approach (which consists of pooling all patients of a treatment regimen and dividing the total number of COPD exacerbations by the total follow-up time).

The number and the percentage of patients with COPD exacerbations, the number of COPD exacerbations and the COPD exacerbation rate per patient per year as above will also be presented by treatment regimen for each of the following types of COPD exacerbation:

- Mild COPD exacerbations (intensity recorded as ‘Mild’ on the form)
- Moderate COPD exacerbations (intensity recorded as ‘Moderate’ on the form)
- Severe COPD exacerbations (intensity recorded as ‘Severe’ on the form)
- Moderate/Severe COPD exacerbations (intensity recorded as ‘Moderate’ or ‘Severe’ on the form)
- COPD exacerbations resulting in death (i.e. COPD-related deaths; serious criteria ‘Results in death’ ticked on the form)
- COPD exacerbations requiring hospitalisation (i.e. serious criteria ‘Requires in-patient hospitalisation or prolongs existing hospitalisation’ ticked on the form).

Additionally (and more generally), the number (%) of patients with COPD exacerbations and the number of COPD exacerbations will be presented by treatment regimen for each of the following category:

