8.6.3.13 Time to next COPD exacerbation

8.6.3.13.1 Time to next COPD exacerbation derived from ‘Acute Exacerbation COPD’ form of the eCRF

See section 8.6.3.11 for the derivation of COPD-related exacerbations.

Time to next COPD exacerbation will be analysed using the Kaplan-Meier method. Patients without a COPD exacerbation or who are discontinued before having it will be considered as “censored” patients.

For the following study periods: [0-4) weeks, [4-8) weeks, [8-12) weeks, [12-16) weeks, [16-20) weeks and [20-26) weeks, the number of COPD exacerbation-free patients at the beginning of the period, the cumulative number of patients with COPD exacerbation at the end of the period and the probability of having experienced a COPD exacerbation at the end of the period with the associate two-sided 95% CIs will be presented by treatment regimen. The point estimates and the relative two-sided 95% CIs will be presented by treatment regimen for the 75th, 50th and 25th percentiles. A Kaplan-Meier plot will also be presented. Comparisons between treatment regimens will be

performed by means of the log-rank test. The p-values of the pairwise log-rank test comparisons will be displayed on the figure.

A similar analysis using the Kaplan-Meier method will be performed for:

- Time to next mild COPD exacerbation (intensity recorded as ‘Mild’ on the form)
- Time to next moderate COPD exacerbation (intensity recorded as ‘Moderate’ on the form)
- Time to next severe COPD exacerbation (intensity recorded as ‘Severe’ on the form)
- Time to next moderate/severe COPD exacerbation (intensity recorded as ‘Moderate’ or ‘Severe’ on the form).

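### Time to next exacerbation is clocked from the day index symptoms stopped, a post-randomisation date that treatment can move, and patients without that date have no computable time

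*SAP*

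**What the plan says.** SAP 7.1.4.10 takes the start of symptoms of the first new exacerbation and subtracts the "Date when current COPD exacerbation symptoms stopped". The event row of Table 4 repeats this: "Time from when current COPD exacerbation symptoms stopped until Date of next COPD exacerbation after entering in study". The three censoring rows (no event, death, withdrawal or loss) keep that origin; the death row reads "Time from when current COPD exacerbation symptoms stopped until Date of death".

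Section 8.6.3.13.1 analyses the result by Kaplan-Meier with pairwise log-rank tests, and 8.8.1 applies the same approach to adjudicated events. Events are selected by 8.6.3.11, whose rule opens "Only COPD exacerbations with symptoms start date" and admits any onset on or after first study treatment. For a partial stop date, 7.2.2.2 sets a missing day to the 15th, but "missing months will be left as missing", and so are years. For a partial onset of a new exacerbation, 7.2.2.4 uses the first of the month. SAP section 6 assigns secondary efficacy endpoints to the ITT population.

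Other endpoints run from first dose. Table 6, for clinical treatment failure, has "Time from initiation of study treatment until Date of clinical treatment failure after entering in study"; Tables 2-1, 2-2 and 3 also start at initiation of study treatment. Protocol 13.4.2 names the endpoint without an origin, and SAP section 9 does not list the origin among the changes from the protocol.

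**The concern.** Patients enter during an active exacerbation, so symptom stop normally falls after randomisation. Protocol 9.2 gives quicker recovery as the purpose of treatment, so an effective regimen would be expected to bring that date forward. Time zero is then itself an outcome. The log-rank test compares arms from origins that treatment may have shifted, among patients selected for having recovered, and the result mixes the length of the index episode with the delay to the next one.

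The definition also fails where the course is worst. A patient who dies, withdraws or reaches Week 26 with symptoms still present has no origin, and Table 4 gives no rule. Elsewhere the SAP foresees such patients: Table 3 censors those who never recover, and Table 5 those never ready for discharge.

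**Working it through.** The documents give no event count, power or effect size for this endpoint. The only planning figure is 85 per regimen for FEV1. It reproduces (100 mL difference, SD 230 mL, two-sided 5%, 80% power: 84.01 by the t calculation, so 85) and serves below only as the arm size.

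**1. The shift in a single pair.** Two patients both have their next exacerbation on Day 60. Index symptoms stop on Day 8 in one and Day 20 in the other. The SAP clock gives 60 - 8 = 52 and 60 - 20 = 40 days; a first-dose clock gives 60 - 1 = 59 for both. The 12-day difference is index duration only. This shows the mechanism for two individuals, not an effect between arms.

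**2. Date rules.** Stop day missing, set to the 15th; onset day missing in the same month, set to the 1st: 1 - 15 = -14 days. No rule handles a negative time. Section 7.2.2.2 is worded for index duration and time to first dosing. If it is not carried over to 7.1.4.10, a missing stop day leaves no time at all. Even with a fully known stop date on day d of the month, a partial onset in that month gives 1 - d, which is negative unless d = 1.

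**3. Size of the bias, by simulation.** Inputs from Protocol 7.1: "A median duration of exacerbation of 13 (6 to 24) days has been reported in patients receiving SoC", and about 32% of exacerbations occurring within 8 weeks of the preceding one. Follow-up is 26 x 7 = 182 days. Assumptions:
- 6 to 24 is read as an interquartile range (the protocol does not say) and duration as lognormal, so sigma = (ln 24 - ln 6)/(2 x 0.6745) = 1.03.
- Duration is counted from first dose.
- Treatment scales every duration by the ratio of the medians.
- Recurrence hazard is either constant, -ln(0.68)/56 = 0.0069 per day, or falling (Weibull shape 0.6, also 32% by day 56).
- 85 per arm, 2000 runs per scenario. Ranges in the table span the two hazards; the 11 v 13 rows use the constant hazard only.

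| Setting | Median index days, treated v control | HR, symptom-stop clock | Rejection | HR, first-dose clock | Rejection |
|---|---|---|---|---|---|
| Next exacerbation on same calendar date | 13 v 13 | 1.00 | 4.6-6.6% | 1.00 | 5.0-6.2% |
| | 11 v 13 | 0.97 | 4.8% | 1.00 | 4.6% |
| | 9 v 13 | 0.94 | 5.0-7.0% | 0.99-1.01 | 4.3-5.6% |
| | 6 v 13 | 0.89-0.91 | 8-10% | 1.00 | 4.8-5.4% |
| Gap after recovery unchanged | 11 v 13 | 1.00 | 4.8% | 1.04 | 4.8% |
| | 9 v 13 | 0.99 | 5.8-6.1% | 1.04-1.06 | 6.2-7.1% |
| | 6 v 13 | 1.00-1.01 | 4.6-4.8% | 1.09-1.12 | 6.5-9.0% |

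With no shift at all, rejection was already 4.6-6.6%, so the 5-7% for a 4-day shift is not clearly above simulation noise. The 8-10% for a 7-day shift is.

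**4. Patients with no stop date.** Under the same distribution, P(duration > 182) = 1 - Phi(ln(182/13)/1.03), about 0.5%, or 0.005 x 85 = 0.4 patients per arm. Deaths and withdrawals before symptom stop, and missing stop dates, come on top; the documents do not quantify them. Planned dropout over the whole study is about 5%, and only those leaving before symptoms stop count.

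**The case against.** The strongest reply is that the origin is a choice of question. The protocol says time to next exacerbation without fixing a start, and the interval from the end of one episode to the start of the next is a natural reading. If treatment leaves that interval unchanged, the symptom-stop clock is neutral, while the first-dose clock shows a hazard ratio of about 1.04-1.12 because a longer index episode counts as event-free time. This stands as a reason to keep the gap time. It does not make the gap time a randomised comparison, since it conditions on having recovered.

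It is also fair that other analyses avoid this origin: exacerbation rates and proportions in 8.6.3.11, and the EXACT-PRO version in 8.6.3.13.2, which runs on fixed study weeks. Protocol 13.5.1 calls all analyses exploratory. This limits the consequence but leaves the definition as it is.

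A reader might infer more than the documents support:
- *Negative times would be routine, because events count from first dose.* The eCRF form asks about exacerbations after the qualifying one had subsided (SAP 7.1.4.13, Criterion 4). Negative times should come mainly from partial dates or inconsistent entry.
- *The week intervals show that the clock was meant to start on Day 1.* They are display intervals, reporting for example "the number of COPD exacerbation-free patients at the beginning of the period". The curve and the test do not depend on them.
- *Slow resolvers drop out.* They have a stop date and are analysed; only patients without a usable one are lost.
- *A sizeable share of each arm has no time.* No figure in the documents supports that.

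**Conclusion.** The point holds as a defect of definition with a modest expected effect. The origin is after randomisation, treatment can move it, no rule covers patients without a stop date, and nothing elsewhere in either document repairs this for the eCRF or adjudicated analysis. Under the stated assumptions, with the calendar date of the next exacerbation unchanged, the spurious hazard ratio is about 0.94 for a 4-day shorter index episode and about 0.9 for 7 days. These values are illustrative: they depend on the assumed duration distribution and on the shift, which the trial would have to show. It would be too strong to say that the endpoint is seriously distorted or that many patients are lost. The structural gap does not depend on how many they are. Because this is a named secondary endpoint and the remedy is cheap, the change should be made.

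**What to change.** In SAP 7.1.4.10, Table 4 and 8.8.1, define the time for the main analysis as symptom start of the first new exacerbation minus date of first study dose, for all ITT patients, with every censoring time from the same origin. Keep the gap from symptom stop as a supportive, non-randomised description in patients with a recorded stop date, and report by arm how many have none.

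Add a floor to the partial-date rule: an imputed onset should not precede first dose (main analysis) or symptom stop (supportive analysis). Without it, the first-of-month rule could still give a negative time, or exclude an event under 8.6.3.11. Record the choice of origin in SAP section 9.

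The cost is SAP wording and one derivation, with no new data. The SAP should state the downside: the first-dose clock includes time in the index episode, which can differ between arms. It therefore answers when the next exacerbation occurs after treatment starts, not how long remission lasts.
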